11.4 Interim Analysis

11.4.1 Primary Endpoint

At each interim analysis, superiority and futility tests on PFS will be conducted as follows.

Superiority: A superiority test is to test if the experimental arm has a longer PFS than the control arm. The first interim analysis for superiority will be conducted when 80 patients progress or complete the 2 years of follow-up. With 6 months of run-in period and a monthly accrual of 15 patients, this will occur at approximately 33 months. After this time, interim analyses will be conducted every six months corresponding with scheduled meetings of the Alliance Data and Safety Monitoring Board (DSMB). The final analysis will be conducted 2 years after the completion of accrual. With the expected study plan, there should be about 4 or 5 interim analyses before the final analysis. The superiority testing during the interim analyses will be using one-sided $\alpha=0.0025$. (A one-sided p-value smaller than 0.5 and a test statistic larger than 0 imply the superiority of the experimental arm.) The final analysis will be using one-sided $\alpha=0.025$. Due to the relatively small number of interim analyses and the small alpha spending at each interim analysis, the overall type I error rate will not be much larger than the nominal one-sided $\alpha=0.025$ (107).

Futility: Futility testing will be conducted at the time of each interim analysis scheduled for a superiority test. We will consider stopping the study early due to futility if the 1-sided p-value is larger than or equal to 0.5 (or the standardized log-rank test statistic is smaller than 0) at any interim analysis.

11.4.2 Progression Rate

The power of the log-rank test depends on the PGR in the two arms. An interim analysis will be conducted when 400 patients are enrolled on the study to check if the specified 20% of 2-year PGR is accurate or not. At the interim analysis, the 2-year PGR of the control arm will be estimated. If the estimate is smaller than 20%, we will recalculate the sample size using the estimated 2-year PGR for the control arm, $HR=0.472$, two sided $\alpha=0.05$ and a power of 80% and consider increasing the sample size by a maximum of 20% of the current sample size. For example, if the estimated 2-year PGR for the control arm is 18%, then we need 466 eligible patients (about 11% increase from 418 eligible patients). In case the observed progression rate is so low that a maximum of 20% increase in sample size does not guarantee a reasonable power for the primary endpoint, we will consider suspending the study for revision.

11.4.3 Accrual Monitoring

The accrual rate will be monitored by DSMB complying with CTEP's Early Stopping Guidelines for Slow Accruing Trials.

11.5 Statistical analyses for substudy 151105

For Objective 10.3.2.1, the expression level of MnSOD, XRCC1 and GST will be correlated with PSADT within each arm. The expression level of these genes may be highly correlated with PSADT in the control arm. However, if dietary modification alters the genetic risk, the association may be insignificant or less significant in the experimental arm.

For Objective 10.3.2.2, the expression level of MnSOD, XRCC1 and GST will be correlated with time to pathological progression using Cox regression method within each arm. The expression level of these genes may be highly correlated with time to pathological progression in the control arm. However, if dietary modification alters the genetic risk, the association may be insignificant or less significant in the experimental arm.

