selenium levels they found that the cohort with the highest selenium levels and AA genotype were protected against prostate cancer in general and clinically aggressive prostate cancer specifically. Another example of genotype environment interaction is vitamin D and Vitamin D Receptor polymorphisms. A study from the Physicians Health Study demonstrated that while the Vitamin D Receptor polymorphism *BsmI* or *FokI* were not associated with prostate carcinoma, men with *FokI ff* genotype and low vitamin D levels had the highest risk of developing PCa in general and aggressive disease specifically (98). Given that vitamin D oral formulations have been explored as a treatment option for PCa (99), identification of an interaction between genotype and environment could have potential clinical application.

The MEAL study offers the ideal population to study the interaction between genetic risk and diet. First and foremost, if genetic risk is associated with aggressive disease, then patients with the high risk genetic background should be more likely to progress. What is unique about the MEAL study is to determine if dietary modification alters that genetic risk. If it does then genetically high risk patients could modify their diet at the time of diagnosis or possibly sooner. Alternatively, if diet does not modify risk of progression then more aggressive management could be instituted.

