10.3.2 Objectives

10.3.2.1 To compare MnSOD, XRCC1, and GST gene polymorphisms to PSADT in AS patients receiving dietary intervention versus no intervention.

10.3.2.2 To compare MnSOD, XRCC1, and GST gene polymorphisms to time to pathological progression in AS patients receiving dietary intervention versus no intervention.

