10.3.3 Methods

Whole blood samples are being collected at baseline for DNA isolation and evaluation of genetic polymorphisms that affect antioxidant metabolism such as MnSOD. In addition, there is evidence of other interactions between antioxidant systems and dietary practice. Some of these could have an impact on the prostate such as catechol-o-methyl transferase and glutathione peroxidase.

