10.4.3 Methods

Institutions will be asked to provide 10 x 5 um unstained sections that show cancer on charged glass slides from the formalin-fixed, paraffin-embedded, diagnostic prostate biopsy blocks to the Alliance Biorepository at The Ohio State University (see Section 6.2). Only one core should be placed on each slide. Label the slides with CALGB 70807 patient ID number, accession number, and order of sections.

The immunohistochemistry will be performed at Roswell Park Cancer Institute, under the direction of [REDACTED]. Commercially available antibodies will be used to immunostain the slides for the following: Ki-67 (proliferation), cleaved caspase 3 (apoptosis), androgen receptor, and 5-alpha reductases 1, 2, and 3. A panel of microRNAs will be extracted from the serum collected as part of sub-study CALGB 151105 (see Section 6.2.3). microRNA 141 and 375 expression will be assayed by procedures developed by Exiqon Laboratories (Blondal et al, 2013).

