10.4.4 Statistical considerations

The baseline biomarkers will be associated with progression-free survival (PFS), time to progression as defined for the main study or death. Specific statistical analysis plans are as follows for each study objective. About 80% of the patients in the main study will participate in this correlative study. With $n = 334 (=418 \times 0.8)$ patients, a Cox regression model to regress PFS on a continuous biomarker will have 95% of power to detect a log-hazard ratio (or, regression coefficient of the Cox proportional hazards model) of 0.4 between two patient groups whose biomarker values are 1 standard deviation away with a two-sided alpha level of 5%. This power calculation is based on 85% of 2-year PFS for the whole population, the accrual and follow-up periods assumed for the main study and the assumption that each marker is normally distributed (possibly after a transformation).

- 10.4.4.1 To compare proliferation, apoptosis and the tumor growth index to dietary intervention assignment as predictors of cancer progression in AS patients**

PFS will be regressed on each biomarker of proliferation (KI-67), apoptosis (cleaved caspase 3) and tumor growth rate (a composite of proliferation and apoptosis) using a Cox regression model. In order to see which biomarkers are independently prognostic, we will also perform a Cox regression to regress PFS on all three of the biomarkers. We will repeat these regression analyses adjusting for treatment allocation to investigate if the effect of these biomarkers is confounded with treatment allocation.

10.4.4.2 To compare proliferation, apoptosis and tumor growth index to outcome predictors among AS patients randomized to dietary intervention as opposed to those assigned to the comparison group

The analyses adjusting for treatment allocation as described in in Section 10.4.4.1 will be repeated by adding the interaction term between each marker and treatment allocation to the regression models to see if the effect of each biomarker is different between the two treatment arms. If any of these interaction terms are significant, then we will also fit a regression model within each arm to develop a prediction model based on the biomarkers for each treatment arm.

10.4.4.3 To compare protein levels of the androgen receptor and 5-alpha reductase 1, 2, and 3 to dietary intervention assignment as predictors of cancer progression in AS patients

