PFS will be regressed on each biomarker of androgen receptor, 5 alpha reductase 1, 5 alpha reductase 2, and 5 alpha reductase 3 using a Cox regression model. In order to see which of these protein level biomarkers are independently prognostic, we will also perform a Cox regression to regress PFS on all four of these biomarkers. We will repeat these regression analyses adjusting for treatment allocation to investigate if the effect of the biomarkers is confounded with treatment allocation.

10.4.4.4 To compare protein levels of the androgen receptor and 5-alpha reductase 1, 2, and 3 as outcome predictors among AS patients randomized to dietary intervention as opposed to those assigned to the comparison group

The analyses adjusting for treatment allocation as described in in Section 10.4.4.3 will be repeated by adding the interaction term between each marker and treatment allocation to the regression models to see if the effect of each biomarker is different between the two treatment arms. If any interaction terms are significant, then we will fit a regression model within each arm to develop a prediction model based on the biomarkers for each treatment arm.

10.4.4.5 To compare expression of microRNAs 141 and 375 to dietary intervention assignment as predictors of cancer progression in AS patients

PFS will be regressed on each biomarker of microRNAs 141 and 375 using a Cox regression model. In order to see which of these microRNAs are independently prognostic, we will also perform a Cox regression to regress PFS on both of the microRNAs. We will repeat these regression analyses adjusting for treatment allocation to investigate if the effect of these biomarkers is confounded with treatment allocation.

The microRNA package we are going to use will examine many more (~200) microRNA biomarkers. We will develop a prediction model for PFS using all the examined microRNA biomarkers as candidate predictors using the gradient lasso procedure,¹¹³ and compare the prediction power of this model with that based on microRNAs 141 and 375. A Cox regression will be conducted including the risk score fitted using the gradient lasso method and treatment allocation.

10.4.4.6 To compare expression of microRNAs 141 and 375 as outcome predictors among AS patients randomized to dietary intervention as opposed to those assigned to the comparison group

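### Section 11.5 gives no between-arm test of whether diet alters genetic risk, and Sections 11.3(2) and 11.5 correlate PSADT on a scale that breaks at zero slope

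*Combined protocol and SAP*

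**What the plan says.** The background to the polymorphism substudy (10.3.1) frames the question as effect modification: "What is unique about the MEAL study is to determine if dietary modification alters that genetic risk". Objective 10.3.2.1 reads "To compare MnSOD, XRCC1, and GST gene polymorphisms to PSADT in AS patients" and contrasts the dietary arm with the comparison arm. Objective 10.3.2.2 does the same for time to pathological progression. The only assay described for these genes (10.3.3) is on DNA: "Whole blood samples are being collected at baseline for DNA isolation and evaluation of genetic polymorphisms".

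The analysis text (11.5) differs in two respects. The predictor becomes expression level, and the analysis is confined to each arm: "the expression level of MnSOD, XRCC1 and GST will be correlated with PSADT within each arm". The second paragraph of 11.5 repeats this with Cox regression. The only stated sign of a diet effect on genetic risk is that "if dietary modification alters the genetic risk, the association may be insignificant or less significant in the experimental arm".

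For the tissue and microRNA markers of the same substudy, 10.4.4.2 repeats the arm-adjusted models by "adding the interaction term between each marker and treatment allocation". Sections 10.4.4.4 and 10.4.4.6 follow the same order, as in "If any interaction terms are significant, then we will fit a regression model within each arm".

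Section 11.3 defines PSADT as log 2 over the least-squares slope of log PSA, from all available values. Item (2) of its plasma carotenoid analyses correlates carotenoids with PSADT by scatter plot and regression. Neither 11.3(2) nor 11.5 states a scale for PSADT or a rule for zero or negative slopes.

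**The concern.** A difference in significance between two arms is not a test of a difference in effect. Each within-arm test has limited power, so an association of identical size will often reach significance in one arm and miss it in the other. The problem is worse for progression: if the diet works, the experimental arm has fewer events, and its association looks weaker without any gene-diet interaction. A report following 11.5 could state that diet modifies genetic risk when it does not.

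The PSADT issue pulls the other way. As slope passes through zero, PSADT jumps from very large positive to very large negative values, so two men with nearly identical stable PSA sit at opposite extremes. A real carotenoid-PSA or genotype-PSA association could be missed.

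**Working it through.** Section 11.5 states no sample size, power or alpha, so there is no figure of its own to reproduce. Effect sizes below are assumptions.

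**Inputs.** Men per arm: 10.4.4 gives 418 × 0.8 = 334, and equal allocation (11.1) gives 167. The 80% participation is stated for the 10.4 markers and is assumed here for 10.3. Control 2-year pathological progression: 10% (the example in 11.3), with 8% as a variant (11.2 gives 8-10%). Diet hazard ratio: ln 0.9 / ln 0.8 = 0.472, as in 11.4.2.

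**1. Progression, same gene effect in both arms.**
- Control events: 167 × 0.10 = 16.7. Experimental rate: 1 − 0.9^0.472 = 4.85%, or 8.1 events. Total: about 25.
- Within-arm power for log-HR b per SD with d events: Φ(b√d − 1.96) + Φ(−b√d − 1.96).
- P(significant in control only) = power_C × (1 − power_E).

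| b per SD | power_C | power_E | control only |
|---|---|---|---|
| 0 | 0.050 | 0.050 | 4.7% |
| 0.1 | 0.069 | 0.059 | 6.5% |
| 0.2 | 0.129 | 0.088 | 11.8% |
| 0.3 | 0.232 | 0.137 | 20.0% |
| 0.4 | 0.373 | 0.207 | 29.6% |
| 0.5 | 0.533 | 0.296 | 37.5% |

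With 8% control progression (13.4 vs 6.4 events), the last three rows become 17.2%, 25.6% and 33.8%. With no diet effect and a 10% rate they are 17.8%, 23.4% and 24.9%. In simulation with about 17 vs 8 events, a two-sided interaction test rejected in 3-5% of trials.

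**2. Correlation with the PSA outcome, same r in both arms.** By Fisher's z with n = 167, within-arm power p is Φ(z√164 − 1.96) + Φ(−z√164 − 1.96), and the control-only pattern has probability p(1 − p). For r = 0.05, 0.10, 0.15, 0.20, 0.25 and 0.30, p = 0.098, 0.250, 0.490, 0.738, 0.905 and 0.977. The pattern occurs in 9%, 19%, 25%, 19%, 9% and 2%.

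**3. PSADT scale.** PSADT = ln 2 / slope. Slopes per year of 0.231, 0.01, 0.001, −0.001 and −0.01 give 3.0, 69, 693, −693 and −69 years.

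The simulation used nine quarterly PSA values per man and an assumed PSA coefficient of variation of 10%. With Sxx = 3.75, the slope SE is 0.10/√3.75 = 0.052 per year. Mean slope was assumed at 0.05, 0.10 or 0.15 per year. The spread was set so that 14% (11.2) exceed ln 2/3 = 0.231. Marker-slope correlation was 0.2 or 0.3.
- Flat or falling PSA: 2-39% of men.
- Power with 167 men: log-PSA slope about 47-97%, Pearson on raw PSADT about 5-9%, Spearman on PSADT 5-59%.
- Power with 400 men: slope 83-100%, Pearson 4-9%, Spearman 5-92%.

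Spearman does poorly because ranking places men with falling PSA below the fastest risers. The 14% is applied to the 24-month slope, not to earlier visits.

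**4. What an interaction test could detect.** For progression, SE = √(1/16.7 + 1/8.1) = 0.428, so the 95% CI for the ratio of hazard ratios is the estimate divided and multiplied by exp(1.96 × 0.428) = 2.3. If diet fully abolishes a control-arm log-HR of 0.3, 0.4 or 0.5, power is 10.8%, 15.4% and 21.5% (9.6%, 13.3% and 18.1% at 8% control progression). For the PSA outcome on the slope scale, simulated power under full abolition is 27-76%.

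**The case against.** Several objections have force.

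- **Expression level is probably a slip.** Objectives and methods both say polymorphisms, and DNA is the only assay described for these genes. This stands: it is a wording correction. A reader might infer that an expression analysis is intended or that the substudy measures no expression at all. Neither follows, since for other markers 10.4.3 says that "microRNA 141 and 375 expression will be assayed".
- **11.5 voices an expectation, not a decision rule.** This also stands. A reader might infer that the plan commits to declaring modification from separate p-values; the word may does not support that. But no other between-arm comparison is named for these objectives.
- **The larger percentages need large effects.** With an assumed allele frequency of 0.3, the genotype SD is √(2 × 0.3 × 0.7) = 0.648, so 0.3-0.5 per SD means hazard ratios of about 1.59-2.16 per allele. At 0.1-0.2 per SD the pattern occurs in 7-12%. The full range must be read, not its upper end.
- **The PSADT method is not named.** The documents specify neither Pearson nor an untransformed scale, and a scatter plot would expose extreme values. True, but the remedy would then be chosen after seeing the data.
- **Two PSADT recipes.** Section 8.4 uses the last three values. A reader might infer that the analysis variable is undefined. Section 11.3 is the analysis section and governs, so this adds little.

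**Conclusion.** The point holds for the correlative objectives and should be corrected. Section 11.5 does not test the question that 10.3.1 poses, and it departs from the approach that 10.4.4 takes for the other markers. With no true modification, the pattern 11.5 describes would appear in about 5-38% of trials for progression over log-HRs of 0 to 0.5 per SD, and in 2-25% for correlations of 0.05 to 0.30. These sizes rest on 167 men per arm and the assumed effects. The missing test rests on the text alone.

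The discontinuity of PSADT follows from its definition. The power loss (about 5-9% against 47-97%) depends on the assumed slope distributions and on use of the raw scale.

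A reader might infer that the primary result is at risk. The documents do not support that from this point: only objectives 10.1.2.2, 10.3.2.1 and 10.3.2.2 are touched. How the PSADT threshold in the primary endpoint treats falling PSA is a separate question, not argued here.

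**What to change.** **Section 11.5.** Replace expression level with genotype, and fix the coding for each gene before genotypes are linked to outcomes. For each gene and outcome, fit one model to both arms with genotype, arm and genotype-by-arm interaction. Use Cox regression for pathological progression, stratified or sparsely adjusted because only about 25 events are expected, and a linear model for the PSA outcome. Report the interaction estimate with its 95% CI; give within-arm estimates as description only.

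**Sections 11.3(2) and 11.5.** Analyse the slope of log PSA (log 2/PSADT) from all available values as in 11.3, excluding values after active treatment begins. Use a mixed model for log PSA or precision-weighted regression. At a 10% coefficient of variation, a man with values only at months 0, 3 and 6 has slope SE 0.10/√0.125 = 0.28 per year, against 0.05 with nine values. If 10% of men have only three values, unweighted power in the least favourable setting falls from 47% to 23%; weighting restores about 43%.

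**Status.** Label 10.3.2.1 and 10.3.2.2 exploratory, and state whether the six interaction tests (three genes, two outcomes) are adjusted for multiplicity. Unadjusted and if independent, the chance of at least one false positive is 1 − 0.95^6 = 26%.

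**Cost.** Text changes and a modest amount of programming; no new data, visits or assays. The plan should state the downside: for 10.3.2.2 interaction power is only about 10-22% even under full abolition of a log-HR of 0.3-0.5 per SD, so a null result will say little.
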